Stroke is the leading cause of disability and death among adults in China, with an annual death toll of approximately 1.5 million and a disability rate of about 75%. About 70% of stroke patients suffer from ischemic stroke, and the recurrence rates at 3 months, 6 months, and 12 months after the first ischemic stroke are approximately 10.9%, 13.4%, and 14.7%, respectively. The risk of death and disability after the recurrence of ischemic stroke is 9.4 times that of the initial stroke. This project increases the sample size based on the existing ischemic stroke follow-up cohort and conducts a 1-year follow-up to observe the recurrence situation, mRs scores, and adverse events after discharge. Combining complex multi-dimensional data such as demographic data, physical examination, medical history, imaging images, medication information, scale scores, CYP2C19 genotype test results, laboratory examinations, etc.; using convolutional neural networks for lesion segmentation of ischemic stroke patient imaging and feature extraction; using Cox regression models to obtain factors influencing recurrence and adverse events; constructing an ischemic stroke recurrence risk prediction model within 1, 3, 6, and 12 months using the XGBoost combined with convolutional neural network algorithm (Convolutional Neural Network, CNN). Exploring the predictive effect of XGBoost on ischemic stroke recurrence risk at different times and providing new ideas and methods for the prevention and control of major chronic diseases.

3. Design Type: Cohort Study.

4. Research Subjects: Inpatients with ischemic stroke from the Department of Neurology at the Second Affiliated Hospital of Nanchang University and more than ten tertiary hospitals in the province.

5. Sample Size: 2400 cases.

6. Inclusion Criteria:

(1) Inclusion criteria:

1) Aged 18-85; 2) Diagnosed with ischemic stroke or transient ischemic attack (diagnosis in line with the standards set by the Cerebrovascular Disease Group of the Neurology Society of the Chinese Medical Association in 2014); 3) Within the acute phase of onset (2 weeks); 4) Voluntarily participate and sign an informed consent form.

(2) Exclusion criteria:

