1) Patients with cancer; 2) Patients with cardiogenic infarction, other causes of cerebral infarction, or stroke of unknown cause; 3) Patients with hemorrhagic stroke, mixed stroke, and tumor stroke; 4) Patients with severe heart, lung, or liver system diseases; 5) Patients judged by researchers to have poor compliance and unable to complete long-term follow-up; 6) Patients currently participating in any clinical trial of investigational drugs or medical devices.

7. Observation Indicators:

Demographic data, physical examination, medical history, imaging images, medication information, scale scores, CYP2C19 gene test results, laboratory examinations, etc., mRS scores, recurrence situation (whether recurrent, number of recurrences, time of recurrence, type of stroke recurrence, etc.), and adverse events (type of adverse event, severity, start time, stop time, etc.) of ischemic stroke patients within 1, 3, 6, and 12 months after discharge.

8. Statistical Analysis Methods:

This study uses SPSS25.0 software for statistical analysis. Measurement data that conforms to the normal distribution are expressed as mean \pm standard deviation (); Measurement data that do not conform to the normal distribution are expressed as median (quartile) [M(Q1, Q3)]; Count data are expressed as frequency and percentage (%). The comparison between count data groups uses the chi-square test or Fisher's exact probability method; the comparison between measurement data groups uses the t-test or Mann-Whitney U test. $P < 0.05$ is considered statistically significant.

9. Modeling Methods:

CNN, Logistic, SVM, RF, XGBoost model construction is implemented using PyCharm (professional v2018.3) software under the Anaconda Python3.6 environment. Data preprocessing uses the numpy (1.20) and Pandas (1.2.0) packages, CNN image processing model construction uses the tensorflow (2.1.1) architecture, data analysis and model construction use Scikit-learn (0.23.1).

Brain imaging feature extraction: Introducing deep convolutional neural network models such as UNet++, FCN, AlexNet, etc., to process brain imaging images, while considering the natural 3D attributes of brain imaging images, using 3D convolution, pooling to capture changes in brain imaging between continuous slices; comparing the effects of different deep convolutional neural network models, selecting the optimal model as the method for extracting brain imaging features.

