Prediction model construction: The variables screened by Cox regression with statistical differences are fused with the imaging features extracted by CNN. The fused data is divided into training sets, validation sets, and test sets, using a ten-fold cross-validation training method, respectively establishing machine learning-based ischemic stroke recurrence risk prediction models (research models: XGBoost; control models: Logistic, SVM, RF) within 1, 3, 6, and 12 months after discharge, continuously optimizing the model effects on the validation set until the optimal.

Model Evaluation: After the model effect reaches the ideal effect, compare the performance evaluation indicators of the research model and the control model on the test set (AUC value, sensitivity, time efficiency, etc.). AUC, sensitivity, and time efficiency are used to evaluate the comprehensive predictive ability, accuracy rate, and prediction efficiency of the model, respectively.

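### The XGBoost comparison has no deciding contrast and no interval for a difference between models, so a lead on point estimates somewhere in the grid is weak evidence that it predicts better

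*Combined protocol and SAP*

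**What the plan says.** In section 9 (Modeling Methods), the paragraph on prediction model construction fixes the roles in advance: "research models: XGBoost; control models: Logistic, SVM, RF". The models are built for recurrence "within 1, 3, 6, and 12 months after discharge". The Model Evaluation paragraph then says to "compare the performance evaluation indicators of the research model and the control model on the test set (AUC value, sensitivity, time efficiency, etc", so the list of measures is open-ended. It adds that "AUC, sensitivity, and time efficiency are used to evaluate the comprehensive predictive ability, accuracy rate, and prediction efficiency of the model, respectively".

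Each named measure therefore has a purpose, but the measures are not ranked. The plan names no main horizon and no main control. It gives no paired test or interval for a difference between models, no adjustment for multiple comparisons, and no rule for saying that one model is better.

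Section 8 (Statistical Analysis Methods) sets a 0.05 significance threshold and lists chi-square, Fisher, t and Mann-Whitney tests for comparing groups. None of these is tied to the comparison of models. The opening summary describes the XGBoost work as exploratory.

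**The concern.** One model is singled out beforehand and set against three others over a grid of horizons and measures, and the plan describes only a comparison of values. All four models would be scored on the same test patients, and the number of recurrences there is modest, so chance alone will reorder equally good models from one cell of the grid to the next. With nothing named as decisive, a lead in one cell can become the study's message although the models do not truly differ. A reader of the results could not tell a planned main finding from the most favourable cell. The practical stake is whether a more complex model is recommended over a simpler one on the strength of noise.

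**Working it through.** **Inputs from the documents.** One research model and three controls; four horizons (1, 3, 6 and 12 months); three named measures plus an open remainder; "Sample Size: 2400 cases"; and recurrence of about 10.9%, 13.4% and 14.7% at 3, 6 and 12 months (opening summary). The plan states no error rate or power for the model comparison, so there is no figure of its own to reproduce.

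**Inputs that must be assumed.** Test-set size, the 1-month recurrence rate, the cut-point for sensitivity, the true AUC, the correlation between models' scores, and how far a model's errors are shared across horizons.

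**Step 1: size of the grid.** 3 controls × 4 horizons = 12 pairwise contrasts on AUC. Adding sensitivity gives 24, and adding time efficiency gives 36, before the open remainder.

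**Step 2: benchmarks if everything were independent.** With four equal models, XGBoost ranks first on a given measure at a given horizon with probability 1/4.
- First on AUC at one or more of four horizons: 1 − 0.75^4 = 0.68.
- At least one significant AUC win for XGBoost among 12 contrasts, each with a 2.5% chance in its favour: 1 − 0.975^12 = 0.26.

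The comparisons share test patients, the XGBoost model and nested outcomes, so independence does not hold and simulation is needed.

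**Step 3: simulation of four models with equal true AUC of 0.70.** Test sets of 240, 480 and 720 (10%, 20% and 30% of 2400); 1-month rate 6%; score correlation between models 0.5 or 0.8; 600 runs per setting. AUC differences were tested by DeLong and sensitivity by exact McNemar. Sensitivity used one fixed threshold, and ties did not count as wins. Run time was left out because it is not sampled from patients. The ranges below span the test-set sizes and score correlations.

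| Share of model-specific error common to all horizons | First of four on AUC at some horizon | First on AUC or sensitivity at some horizon | Significant AUC win over some control |
|---|---|---|---|
| 0 | 60–69% | 74–82% | 21–25% |
| 0.5 | 55–61% | 66–71% | 17–24% |
| 0.95 | 43–48% | 55–61% | 14–19% |

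In the same runs:
- A significant win on AUC or sensitivity somewhere occurred in 18–30%.
- A significant AUC win over all three controls at one horizon occurred in about 1% or less.
- XGBoost was numerically ahead of at least one control on AUC or sensitivity somewhere in 95–100%.

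**Step 4: a second set of assumptions.** 480 test patients; 1-month rate 5.45%; score correlation 0.8–0.9; noise correlation between horizons 0.3–0.9; sensitivity from flagging the top 20%, with ties counted as wins; 800 runs per setting. First on AUC at some horizon: 45–63%. First on AUC or sensitivity: 71–86%.

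Together the two sets give 55–86% for AUC or sensitivity and 43–69% for AUC alone.

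**Step 5: what a deciding contrast achieves.** With one contrast named in advance and a paired two-sided 95% interval, equal models give a false XGBoost win 2.5% of the time. Naming the contrast without the interval is not enough: on point estimates XGBoost would still lead one equal control about 50% of the time.

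**Step 6: precision at 12 months.** Assume 480 test patients: 480 × 0.147 ≈ 71 events and 409 non-events. At AUC 0.70 the Hanley-McNeil standard error of one AUC is about 0.037. The standard error of a paired difference is 0.037 × √(2(1 − r)), about 0.023 when the correlation r between AUCs is 0.8 and 0.016 when it is 0.9. Multiplying by 1.96 + 0.84 = 2.80 gives a true gap of about 0.046–0.065 for 80% power.

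**The case against.** The strongest reply is that the plan promises no claim of superiority. Its summary calls the work exploratory, Model Evaluation asks only for a comparison, and reporting models by horizon is what that aim calls for. Harm arises only if the authors pick the best cell and headline it, which the plan does not tell them to do. This stands in part: it limits how serious the point is. It does not remove it, because XGBoost is fixed beforehand as the research model, and exploratory wording supplies neither a main result nor a measure of uncertainty for the differences.

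A reader might infer that a run-time advantage alone could count as XGBoost being better. The documents do not support that. Model Evaluation assigns time efficiency to prediction efficiency and AUC to overall predictive ability. Nor should being fastest be added to the probabilities above as a one-in-four chance, since run time depends on algorithm, software and hardware.

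A reader might also treat the 36 contrasts as independent tests and conclude that a significant win is likely. Independence would give 1 − 0.975^36 = 60% in XGBoost's favour, but the contrasts are strongly dependent and run time is not a patient-sampled quantity. The simulated figures are far lower.

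Finally, choosing Logistic and 12 months as decisive is a convention. That is correct: the plan lists three controls and is interested in several horizons. Another choice made in advance would serve equally well for error control.

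**Conclusion.** The point holds as an inexpensive improvement to an exploratory comparison, not as a fatal flaw. The missing deciding contrast and the missing interval are plain from the text.

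The size of the problem depends on how a win is read. On point estimates, the kind of comparison the plan describes, a first place for XGBoost on AUC or sensitivity somewhere is more likely than not when the models are equal. On AUC alone it is close to an even chance, and falls below half when errors are largely shared across horizons. On significance, a spurious AUC win is several times more frequent than the nominal 2.5% but remains a minority outcome, so it would be wrong to say that equal models usually yield a significant win.

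All percentages rest on the assumed quantities listed in the working. They changed little with test-set size and more with how far errors are shared across horizons. The true AUC and the 1-month rate were held fixed in the tabulated runs, so sensitivity to those two was not examined there.

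**What to change.** Add one paragraph to Model Evaluation:

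- Make AUC on the test set the main measure, and name one deciding contrast before the test set is examined. XGBoost versus Logistic at 12 months is a reasonable example: Logistic is the simple comparator and 12 months has the most events.
- Report the AUC difference with a paired 95% interval (DeLong or bootstrap). Call XGBoost better only if the interval excludes zero in its favour.
- Report all other horizons, controls and measures in full as secondary, with paired intervals for AUC and sensitivity, and state the cut-point at which sensitivity is taken.
- Keep run time descriptive, consistent with the role the plan already gives it.

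This needs no extra patients, data or follow-up. It has two costs. A favourable result elsewhere in the grid can no longer be the headline. The deciding comparison may also be inconclusive: with about 71 events in an assumed 480 test patients, only an AUC gap of roughly 0.05–0.065 would be detected reliably.

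### AUC is given the role of overall predictive ability for recurrence risk models, but it measures ranking only, and no check of predicted against observed risk is pre-specified

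*Combined protocol and SAP*

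**What the plan says.** The opening summary of the combined protocol and SAP describes the product as "constructing an ischemic stroke recurrence risk prediction model within 1, 3, 6, and 12 months". In section 9 (Modeling Methods), the paragraph on prediction model construction lists the competing methods: "research models: XGBoost; control models: Logistic, SVM, RF) within 1, 3, 6, and 12 months after discharge". Models are tuned by "continuously optimizing the model effects on the validation set until the optimal", with no criterion given for what is optimal.

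The Model Evaluation paragraph then says to "compare the performance evaluation indicators of the research model and the control model on the test set (AUC value, sensitivity, time efficiency, etc", an open list. The sentence after it gives each named measure a role: "AUC, sensitivity, and time efficiency are used to evaluate the comprehensive predictive ability, accuracy rate, and prediction efficiency of the model, respectively".

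No section names a calibration plot, intercept or slope, an observed-to-expected ratio, a Brier score, specificity, a risk cut-off or recalibration. The 0.05 significance level in section 8 is given for group comparisons. No test or margin is given for comparing models.

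**The concern.** A risk model makes two separate claims: that patients who will have a recurrence are ranked above those who will not (discrimination), and that the stated risks match the observed frequencies (calibration). AUC addresses the first only, yet the plan treats it as the measure of overall predictive ability. This is more than a missing detail, because the plan states a role that AUC cannot fill.

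The other two named measures do not fill it either. Sensitivity with neither a stated cut-off nor specificity can rise simply because risks are overstated. Time efficiency, read here as computing time, has no bearing on accuracy.

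The gap matters in this comparison because the four methods need not produce scores on one scale. An SVM natively returns a margin, not a probability, and forests or boosted trees can return distorted probabilities depending on how they are fitted. At stake is whether the comparison can support any statement about the accuracy of the predicted risks.

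**Working it through.** **Inputs from the document.** The opening summary states that "the recurrence rates at 3 months, 6 months, and 12 months after the first ischemic stroke are approximately 10.9%, 13.4%, and 14.7%, respectively"; it gives no 1-month rate. The sample size is "5. Sample Size: 2400 cases", without a derivation. The plan gives no target AUC or calibration figure, so there is no figure of its own to reproduce.

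**Step 1: AUC is unchanged by distortion (exact, no assumptions).** For a patient i with recurrence and a patient j without, AUC = P(s_i > s_j) + ½P(s_i = s_j). If g is strictly increasing, then g(s_i) > g(s_j) exactly when s_i > s_j. So AUC computed on g(s) equals AUC computed on s.

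**Step 2: how far risks can move while AUC stays fixed (illustration).** Assumptions not in the plan: one standard normal predictor x, logit(p) = a + 0.9x, with a set so that the mean risk is 14.7%. The distorted version multiplies every patient's odds by 0.853/0.147 = 5.80, which is the effect of weighting the two classes to balance. As a hand check, a patient with a correct risk of 14.7% has odds 0.147/0.853 = 0.172; 0.172 × 5.80 = 1.00, which is a stated risk of 50%.

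Results with 400,000 simulated patients:

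| | Correct risks | Odds × 5.80 |
|---|---|---|
| AUC | 0.726 | 0.726 |
| Mean predicted risk | 14.7% | 44.5% |
| Brier score | 0.114 | 0.211 |
| Sensitivity at an assumed cut-off of 0.5 | 0.05 | 0.67 |

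Giving every patient 14.7% yields a Brier score of 0.147 × 0.853 = 0.125, so on that score the distorted version is worse than no model. Numerical integration in place of simulation gives AUC 0.728 for both versions, mean risks of 14.7% and 44.5%, and Brier scores of 0.113 and 0.211, which agrees within simulation error.

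**Step 3: other distortions.** With slope 0.95 and the same 14.7% rate, AUC is 0.738 for each of the following:
- correct risks: mean 14.7%, Brier 0.112
- odds × 5.8: mean 44.0%, Brier 0.208
- log-odds spread tripled: mean 27.0%, Brier 0.170
- risks divided by 3: mean 4.9%, Brier 0.128

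At the 3-month rate of 10.9%, AUC is 0.737 for all four versions, with mean risks from 3.6% to 43.3%.

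**Step 4: the measures can point in opposite directions.** In the same set-up at 14.7%, the odds × 5.8 version (AUC 0.738, Brier 0.208) is ahead of a calibrated model with a slightly noisier predictor (AUC 0.727, Brier 0.114) on AUC, and on sensitivity at 0.5 (0.677 against 0.048). The Brier score reverses the order.

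**Step 5: information available for calibration.** If 14.7% applied to all patients, 2400 × 0.147 = 353 recurrences would be expected by 12 months. The plan does not state the size of the test set. If it is 10% to 20% of the cohort (assumed), it would hold 240 × 0.147 = 35 to 480 × 0.147 = 71 recurrences. Under the Step 2 model, the estimated calibration slope of a perfectly calibrated model would have a 95% range of 0.53 to 1.54 with 240 patients and 0.67 to 1.37 with 480.

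**The case against.** The strongest reply is that the plan's list of measures is open, so nothing forbids a calibration analysis. The summary also presents the work as exploratory, and a comparison that includes an SVM and uses sensitivity could be meant as a ranking or classification exercise, for which discrimination is the natural measure. The first part stands: the defensible statement is that calibration is not pre-specified, not that it is excluded. The second part stands only in part, because the plan repeatedly calls the product a risk prediction model and gives AUC the overall role.

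The illustration also has limits. It compares a model with a reweighted copy of itself, not XGBoost with its controls. The plan does not mention class weighting, and weighting could be applied to the logistic model too. Boosted trees fitted to a log-loss target the same likelihood as logistic regression, and the plan states no objective function. Recalibration would remove a constant shift in the odds. All of this stands: the figures show what AUC cannot see, and they do not estimate any error in this study.

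A reader might infer three stronger things that the documents do not support:
- **A badly calibrated model will be declared best.** No rule for choosing a winner is written; the plan only says to compare indicators.
- **Patients will be harmed by wrong risks at the bedside.** No clinical deployment, treatment threshold or clinician-facing probability is planned.
- **XGBoost in particular will overstate risk about threefold.** That size comes wholly from the assumed weighting.

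**Conclusion.** The point holds as a gap in the evaluation plan. The Model Evaluation paragraph assigns AUC a role it cannot fill, and none of the named measures compares predicted with observed recurrence risk. The planned comparison can show which model ranks patients better at each horizon, but not which gives accurate risks. The invariance of AUC is exact. The size of the illustrated gap rests on an assumed predictor, slope and class weighting, and the sensitivity contrast also rests on an assumed 0.5 cut-off. The cohort and its data collection are unaffected, and the remedy is a cheap improvement.

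**What to change.** In the Model Evaluation paragraph of section 9:

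1. Describe AUC as a measure of discrimination.
2. At each of the four horizons and for all four models, add from the same test-set predictions the Brier score, the calibration intercept and slope, and a calibration plot. Give confidence intervals, and state how patients censored before the horizon are handled.
3. Convert SVM margins, and any reweighted scores, to probabilities using training or validation data only, never the test set. Cross-validated predictions are one way; they also limit reuse of the validation set on which the models are tuned.
4. Limit any statement that XGBoost is the better risk model to what discrimination and calibration both support. A fixed rule combining AUC and Brier score is not needed.

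**Cost.** No new patients or data. The output is 4 models × 4 horizons = 16 plots and 16 × 3 = 48 statistics, plus the censoring and probability-conversion steps, so the extra analysis is modest but not trivial. Calibration estimates will be imprecise with about 35 to 71 test-set recurrences at 12 months (assumed split), and more so at earlier horizons, which is why intervals are needed. XGBoost may look less favourable than on AUC alone.
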